16 HOW SUPPLIED/STORAGE AND HANDLING

SPIRIVA HANDIHALER consists of SPIRIVA capsules and the HANDIHALER device. SPIRIVA capsules contain 18 mcg of tiotropium and are light green, with the Boehringer Ingelheim company logo on the SPIRIVA capsule cap and TI 01 on the SPIRIVA capsule body, or vice versa.

The HANDIHALER device is gray colored with a green piercing button. It is imprinted with SPIRIVA HANDIHALER (tiotropium bromide inhalation powder), the Boehringer Ingelheim company logo. It is also imprinted to indicate that SPIRIVA capsules should not be stored in the HANDIHALER device and that the HANDIHALER device is only to be used with SPIRIVA capsules.

SPIRIVA capsules are packaged in an aluminum/aluminum blister card and joined along a perforated-cut line. SPIRIVA capsules should always be stored in the blister and only removed immediately before use. The drug should be used immediately after the packaging over an individual SPIRIVA capsule is opened.

The following packages are available:

- carton containing 5 SPIRIVA capsules (1 unit-dose blister card) and 1 HANDIHALER inhalation device (NDC 0597-0075-75) (institutional pack)
- carton containing 30 SPIRIVA capsules (3 unit-dose blister cards) and 1 HANDIHALER inhalation device (NDC 0597-0075-41)
- carton containing 90 SPIRIVA capsules (9 unit-dose blister cards) and 1 HANDIHALER inhalation device (NDC 0597-0075-47)

Keep out of reach of children. Do not get powder into eyes.

Storage

Store at 25°C (77°F); excursions permitted to 15° to 30°C (59° to 86°F) [see USP Controlled Room Temperature].

The SPIRIVA capsules should not be exposed to extreme temperature or moisture. Do not store SPIRIVA capsules in the HANDIHALER device.

17 PATIENT COUNSELING INFORMATION

Advise the patient to read the FDA-approved patient labeling (Patient Information and Instructions for Use).

Paradoxical Bronchospasm:

Inform patients that SPIRIVA HANDIHALER can produce paradoxical bronchospasm. Advise patients that if paradoxical bronchospasm occurs, patients should discontinue SPIRIVA HANDIHALER.

Worsening of Narrow-Angle Glaucoma:

Instruct patients to be alert for signs and symptoms of narrow-angle glaucoma (e.g., eye pain or discomfort, blurred vision, visual halos or colored images in association with red eyes from conjunctival congestion and corneal edema). Instruct patients to consult a physician immediately should any of these signs and symptoms develop.

Inform patients that care must be taken not to allow the powder to enter into the eyes as this may cause blurring of vision and pupil dilation.

Since dizziness and blurred vision may occur with the use of SPIRIVA HANDIHALER, caution patients about engaging in activities such as driving a vehicle or operating appliances or machinery.

Worsening of Urinary Retention:

Instruct patients to be alert for signs and symptoms of urinary retention (e.g., difficulty passing urine, painful urination). Instruct patients to consult a physician immediately should any of these signs or symptoms develop.

Not for Acute Use:

Instruct patients that SPIRIVA HANDIHALER is a once-daily maintenance bronchodilator and should not be used for immediate relief of breathing problems (i.e., as a rescue medication).

Instructions for Administering SPIRIVA HANDIHALER:

Instruct patients on how to correctly administer SPIRIVA capsules using the HANDIHALER device [see Patient Counseling Information (17)]. Instruct patients that SPIRIVA capsules should only be administered via the HANDIHALER device and the HANDIHALER device should not be used for administering other medications. Remind patients that the contents of SPIRIVA capsules are for oral inhalation only and must not be swallowed.

Instruct patients always to store SPIRIVA capsules in sealed blisters and to remove only one SPIRIVA capsule immediately before use or its effectiveness may be reduced. Instruct patients to discard unused additional SPIRIVA capsules that are exposed to air (i.e., not intended for immediate use).

Distributed by: Boehringer Ingelheim Pharmaceuticals, Inc. Ridgefield, CT 06877 USA

Address medical inquiries to: [contact] or [contact] TTY.

SPIRIVA® and HANDIHALER® are registered trademarks and are used under license from Boehringer Ingelheim International GmbH.

Copyright © 2016 Boehringer Ingelheim International GmbH ALL RIGHTS RESERVED

IT1600AGA72016 10004551/13

IT5300J 75740-09

AUC _{0-4h} Heart Rate	Area Under the Heart Rate Curve (AUC) up to 4 Hours		
AUC _{0-4h} Pulse Rate	Area Under the Pulse Rate Curve (AUC) up to 4 Hours		
BMI	Body Mass Index		
BP	Blood Pressure		
CAS	Completer Analysis Set		
C _{max}	Maximum Observed Plasma Drug Concentration		
CI	Confidence Interval		
CL/F	The apparent clearance		
COPD	Chronic Obstructive Pulmonary Disease		
CV	Coefficient of Variation		
DPI	Dry Powder Inhaler		
DRM	Data Review Meeting		
ECG	Electrocardiogram		
FAS	Full Analysis Set		
FEV ₁	Forced Expiratory Volume in One Second		
FRC	Functional Residual Capacity		
HIV	Human Immunodeficiency Virus		
K _{el}	The First Order Apparent Elimination Rate Constant		
KG	Kilogram		
LLOQ	Lower Limit of Quantification		
MedDRA	Medical Dictionary for Regulatory Activities		

PK	Pharmacokinetic
PT	Preferred Term
QTcF	QT interval corrected using Fridericia's formula
R _{aw}	Airway Resistance
RV	Residual Volume
SAF	Safety Analysis Set
SAP	Statistical Analysis Plan
SD	Standard Deviation
SEM	Standard Error of Mean
sG _{aw}	Specific Airway Conductance
SOC	System Organ Class
t _{1/2}	Terminal Elimination Half-Life
TEAE	Treatment Emergent Adverse Event
TLC	Total Lung Capacity
t _{max}	Time of the Maximum Observed Plasma Drug Concentration
V _z /F	The (Apparent) Volume of Distribution
WHO Drug	World Health Organization Drug Dictionary

1 INTRODUCTION

This document details the statistical analysis of the data that will be performed for the Verona Pharma Plc study: A Phase II, Randomised, Double Blind, Placebo Controlled, Three way Crossover Study to Assess the Bronchodilator Effect of RLP554 Administered in Addition to Open Label Tiotropium in Patients with Chronic Obstructive Pulmonary Disease (COPD).

The proposed analysis is based on the contents of the Final Version of the protocol, Version 2.0 (dated 26 April 2017). In the event of future amendments to the protocol, this statistical analysis plan (SAP) may be modified to account for changes relevant to the statistical analysis.

The table, listing and figure shells are supplied in a separate document.

2 STUDY OBJECTIVES AND DESIGN

2.1 Study Objectives

The primary objective of the study is to investigate the bronchodilator effect on peak forced expiratory volume in one second (FEV₁) (measured in first 4 hours after dosing) and average (measured as the area under the curve (AUC)) FEV₁ over 12 hours of nebulised RPL554 dosed twice daily for 3 days (five total doses), as compared to placebo, when administered in addition to once daily tiotropium.

The secondary objectives of the study are:

- To investigate the effect of twice daily nebulised doses of RPL554, as compared to placebo, when administered in addition to tiotropium on lung volumes
- To assess the bronchodilator effect on peak FEV₁ (measured in first 4 hours after dosing) and average (measured as the AUC) FEV₁ over 12 hours of nebulised RPL554 after the first dose as compared to placebo, when administered in addition to tiotropium
- To analyse plasma concentrations and assess the steady state pharmacokinetics of RPL554 when administered in addition to tiotropium
- To assess the tolerability and safety of twice daily nebulised doses of RPL554 in addition to tiotropium
- To assess the dose response of two different doses of RPL554 on peak, average (0 to 12 hours), and morning trough FEV_1 on Day 3 when dosed in addition to tiotropium
- To determine the onset of action of RPL554 when administered with tiotropium (after the first dose)
- To investigate the bronchodilator effect on nebulised RPL554, or placebo, administered in addition to tiotropium on average FEV₁ over 4 hours after each morning dose

• To investigate the effects of RPL554 on specific airway conductance (sG_{aw}) and lung volumes (residual volume [RV], functional residual capacity [FRC]) when administered in addition to tiotropium.

The exploratory objectives are:

- To examine the effect of RPL554 on top of tiotropium on average FEV₁ over 24 hours after 3 days of dosing
- To assess morning trough FEV₁ prior to the final dose of study treatment.

2.2 Study Endpoints

The primary endpoints of the study are:

• Peak FEV₁ (measured in first 4 hours after dosing) and AUC_{0-12h} FEV₁. These will be measured after dosing on Day 3.

The secondary endpoints are:

- Determination of AUC_{0-4h} FEV₁ after morning dosing
- Peak FEV₁ (measured in first 4 hours after dosing) and AUC_{0-12h} FEV₁. These will be measured after dosing on Day 1
- Determination of onset of action (>10% increase in FEV₁, from pre-first dose, censored at 120 minutes) on Day 1
- RV, FRC, and sG_{aw} at 1.25 hours after dosing on Day 2
- RPL554 steady state pharmacokinetics (AUC, maximum observed concentration (C_{max}), time to maximum concentration (t_{max}), half-life)
- Safety and tolerability:
 - Continuous monitoring of adverse events
 - Laboratory safety tests [haematology, biochemistry and urinalysis]
 - 12-lead electrocardiogram (ECG) (including QT interval corrected using Fridericia's formula (QTcF) and heart rate), supine vital signs [blood pressure and pulse rate]
 - Peak (measured in first 4 hours after dosing) and AUC_{0-4h} pulse rate for each treatment period
 - Holter monitor results

The exploratory endpoints are:

- Pre-dose FEV₁ on Day 3

2.3 Study Design

This is a phase IIb, randomised, double blind, placebo controlled, complete block three-way crossover study to investigate treatment with nebulised RPL554 and tiotropium together in patients with moderate to severe COPD. It is planned to randomise up to 30 patients to have 24 evaluable patients at one study centre. The study comprises the following: screening, three treatment periods each lasting 3 days and an end of study visit.

2.4 Visit Structure

The visit structure and scheduled assessments are detailed in the study protocol section 6.

3 SAMPLE SIZE

This is a complete block three-way crossover study. Assuming a residual coefficient of variation (CV) of 6% for peak FEV₁, 24 patients will give an 80% power to detect a pairwise difference in peak FEV₁ of 5.1%. Assuming a mean baseline FEV₁ of 1.3 litres this will correspond to a difference of about 66mL. The detectable difference for FEV₁ AUC_{0-12h} is expected to be similar as for the peak.

4 RANDOMISATION

All patients consented will be assigned a screening number using the study centre's standard convention.

Patients will receive three different treatment combinations (dry powder inhaler (DPI) plus nebulised treatment) shown in Table 1 in a randomised sequence during Treatment Periods 1 to 3. All study treatments will be administered using the inhaled route. In each case, the DPI treatment will be administered first, followed immediately (within 2 minutes) by the nebulised RPL554 or placebo using a standard Jet nebuliser (PARI LC SPRINT® attached to a PARI TurboBOY® SX compressor unit). The DPI treatment will be open label and the nebulised treatment will be double blind.

TREATMENT	DPI TREATMENT	NEBULISED			
COMBINATION		TREATMENT			
1	Tiotropium 18 mcg qd	RPL554 6 mg bid			
2	Tiotropium 18 mcg qd	Placebo bid			
3	Tiotropium 18 mcg qd	RPL554 1.5 mg bid			
Abbreviation: bid=twice daily; DPI=dry powder inhaler; qd=once daily					

Table 1: Treatment Combinations in RPL554-CO-202

Patients will be equally randomised to one of six treatment sequences (using a Latin Square design with the three different potential medication combinations) before the first study treatment administration in Treatment Period 1.

Tiotropium will be provided in trade dress and will not be blinded.

RPL554 and placebo will be administered double blind. It has not been possible to completely match the placebo to RPL554, as the visual appearance is slightly different. The study personal preparing the RPL554 and placebo, placing them into the nebuliser, and supervising dosing will therefore not to blinded to treatment identity. The dosing cup on each nebuliser will be obscured with tape to visually blind the study treatment. The sponsor, Investigator (defined as Principal Investigator and all study physicians), all patients and all other research personnel (except

bioanalytical personnel performing the pharmacokinetic assays) will therefore be blinded to the treatment allocation.

The blind should be broken only if specific emergency treatment would be dictated by knowing the treatment status of the patient. If the blind needs to be broken, the Investigator should discuss it with the Sponsor's Medical monitor in advance.

Otherwise, all blinding will be maintained until all queries are resolved and the database is locked.

5 INTERIM ANALYSIS

No formal interim analysis is planned for this study.

6 ANALYSIS PLAN

6.1 General

Summary statistics for continuous variables will consist of number of non-missing observations (n), mean, standard deviation (SD), minimum, median and maximum, unless specified otherwise. The precision of these variables is defined in the table, figure and listing shells document.

For categorical variables, the number and percentage of patients in each category will be presented, based on the number of non-missing observations apart from disposition of patients, protocol deviations, background and demographic characteristics, prior and concomitant medications/procedures and adverse events where the percentage will be based on the number of patients in the analysis set.

All statistical tests will be performed using a two-tailed 5% overall significance level, unless otherwise stated. The null hypothesis at all times will be that the treatments are equivalent. All comparisons between the treatments will be reported with 95% confidence intervals for the difference.

6.2 Derived data

• Definition of baseline

Baseline is defined as the last non-missing value (including scheduled and unscheduled assessments) prior to the patient receiving study treatment for each of the respective study treatments.

For ECG and vital signs, time-matched baselines from Day 1 of each Treatment Period will be used for the analysis of data.

Incomplete dates

For calculation purposes, incomplete dates will be completed using worst case. Further details are detailed in the relevant sections as required.

• Non-numeric values for numeric variables

In the case where the result of a variable is recorded as ">x", " \ge x", "<x" or " \le x", then for analysis purposes a value of x will be taken. Where a range of values is quoted the midpoint of the range will be taken.

• Methods for handling withdrawals and missing data

Patients withdrawn after only one treatment period will not be included in the efficacy analyses. If a patient has baseline data missing for a parameter, within a treatment period, data for that patient and parameter will not be derived or analysed for that treatment period.

No imputation of missing data will be performed.

All available data from all dosed patients who have received study treatment will be listed and summarised. Any unscheduled or unplanned readings will be presented within the patient listings, but only the scheduled readings will be used in any summaries. If a treatment day is rescheduled due to variability in FEV_1 or other reason, the rescheduled treatment day will be listed and summarised as the valid treatment day.

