7.4.2.1 Haematology

The following will be measured at screening, on Day 4 of each treatment period and at the end of study visit: Haemoglobin, haematocrit, total white cell count, leukocyte differential count and platelet count.

At each timepoint, a sample of venous blood will be collected in a collection tube containing ethylenediaminetetraacetic acid (EDTA).

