7.4.6 Holter Monitoring

12-lead Holter monitors will be used to perform 24 hour Holter monitoring. A Holter monitor will be placed at screening, monitoring will be ambulatory and will be recorded as an outpatient and the monitor will be removed at the study centre after 24 hours. The screening Holter report must have a minimum of 18 hours recording that is evaluable for rhythm analysis and the report must be reviewed to assess inclusion criteria prior to randomisation.

A Holter monitor will also be placed at least 30 minutes pre-dose on Day 2 of each treatment period and removed after at least 24 hours post-dose and pre-dose on Day 3.

Holter readings will be sent to a central vendor for interpretation.

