10.4.7 Safety

Safety data including safety laboratory tests, 12-lead ECG and Holter parameters, vital signs and physical examinations, will be summarised by treatment group and time point of collection, when appropriate. For continuous variables, the change from baseline (pre-dose at each treatment visit) to each post-dose time point will also be calculated and summarised. Data will further be illustrated by shift tables (showing changes from low/normal/high) and shift plots for selected time points. Separate listings will be generated of abnormal values occurring after the first dose of study treatment.

Coded adverse event terms will be presented by system organ class (SOC) and preferred term and summarised by treatment group. A summary table by treatment group with total number and number of patients with adverse events, SAEs, adverse events leading to discontinuation of study treatment, causally related adverse events and severe adverse events will be produced. Further SAEs, causally related adverse events and adverse event of each intensity will be summarised by SOC and preferred term.

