6.18 SAFETY EVALUATION

Safety and tolerability will be assessed by assessments including physical examinations, vital signs, 12-lead ECGs, 24-Hour Holter monitoring, adverse event recording and laboratory safety tests.

Safety data will be summarised by treatment group and time point of collection when appropriate. For continuous variables, the change from baseline (pre-dose at each treatment day) to each post-dose time point will also be calculated and summarised. Data will further be illustrated by shift tables (showing changes from low/normal/high)

and shift plots for selected time points. Separate listings will be generated of abnormal values occurring after the first dose of study treatment.

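### Haematology, biochemistry and Holter have no pre-treatment value within any period, so SAP 6.2 read literally takes the previous treatment's result as baseline in Periods 2 and 3

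*SAP*

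**What the plan says.** SAP 6.2 (Derived data) sets one general rule: "Baseline is defined as the last non-missing value (including scheduled and unscheduled assessments) prior to the patient receiving study treatment". The sentence goes on to apply it "prior to the patient receiving study treatment for each of the respective study treatments", so baseline is re-set for each period. One exception follows: "For ECG and vital signs, time-matched baselines from Day 1 of each Treatment Period will be used". Laboratory and Holter data stay under the general rule.

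On the schedule, protocol 7.4.2.1 says of haematology: "The following will be measured at screening, on Day 4 of each treatment period and at the end of study visit". Protocol 7.4.2.2 gives biochemistry the same times. Protocol 6.4.3 places the Day 4 sample 24 hours after the Day 3 morning dose, which is the last of the period. For Holter, protocol 7.4.6 says: "A Holter monitor will also be placed at least 30 minutes pre-dose on Day 2 of each treatment period". The monitor comes off before dosing on Day 3. The only other Holter is at screening.

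On outputs, protocol 10.4.7 opens with "Safety data including safety laboratory tests, 12-lead ECG and Holter parameters" and then requires change from baseline for continuous variables and low/normal/high shift tables. SAP 6.18 repeats this: "the change from baseline (pre-dose at each treatment day) to each post-dose time point will also be calculated and summarised". The measure-specific sections ask for less. SAP 6.18.2 plans observed haematology and biochemistry values, and SAP 6.18.5 plans Holter listings and summaries of selected parameters. Neither names a change or a shift.

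**The concern.** A baseline in a crossover should describe the patient off treatment. Here the rule and the schedule together supply, in two periods of three, the result recorded on or just after a different treatment. The change for that period is then the current treatment minus the previous one, both measured at the same point of their own periods.

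Placebo would show a movement opposite to any drug effect. In a shift table, a patient pushed out of range by one treatment would enter the next period as abnormal at baseline and could appear to improve.

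Safety and tolerability is a secondary objective, and laboratory tests and Holter results are listed among the secondary endpoints (protocol 10.3.2, SAP 2.2).

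**Working it through.** The plan gives no figure on laboratory or Holter baselines. Its only calculation, the sample size, concerns peak FEV1 and does not enter here.

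**Step 1: which value the rule selects.**

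| Measure | Period 1 baseline | Period 2 baseline | Period 3 baseline |
|---|---|---|---|
| Haematology, biochemistry | Screening | Period 1 Day 4 | Period 2 Day 4 |
| Holter | Screening | Period 1 Day 2-3 | Period 2 Day 2-3 |

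The Day 2 Holter is placed before that morning's dose but after both Day 1 doses, so it is not a pre-treatment record of its own period either. Urinalysis is taken only at screening and end of study (protocol 7.4.2.3) and is not affected. FEV1, ECG and vital signs have a Day 1 pre-dose reading in each period, so this gap does not arise for them.

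**Step 2: is drug still present?** With the half-life of 8 to 13 hours given in protocol 1.1, the fraction left 24 hours after the last dose is 0.5^(24/8) = 12.5% to 0.5^(24/13) = 27.8%. After the shortest washout of 7 days it is at most 0.5^(168/13), about 0.01%. The patient has washed out by the next period, but the recorded baseline dates from before the washout.

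**Step 3: size of the distortion.** Let d6 and d1.5 be the true effects versus placebo at the time of the Day 4 sample or the Holter. Assume equal numbers completing each of the six sequences, no period drift, full return to the off-treatment level in washout, and screening at that level. Each treatment comes first in 2 of the 6 sequences and directly follows each of the other two treatments in 2. The expected baselines are therefore:

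- placebo: (2 × 0 + 2 × d6 + 2 × d1.5)/6 = (d6 + d1.5)/3
- 1.5 mg: (2 × 0 + 2 × 0 + 2 × d6)/6 = d6/3
- 6 mg: (2 × 0 + 2 × 0 + 2 × d1.5)/6 = d1.5/3

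Expected changes are -(d6 + d1.5)/3 for placebo, d1.5 - d6/3 for 1.5 mg and d6 - d1.5/3 for 6 mg. The differences from placebo are:

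- 6 mg: d6 - d1.5/3 + (d6 + d1.5)/3 = 4/3 × d6
- 1.5 mg: d1.5 - d6/3 + (d6 + d1.5)/3 = 4/3 × d1.5

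The documents give no value for d6 or d1.5, so the table sets d6 = 1 and varies d1.5:

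| d1.5 | Placebo change (true 0) | 1.5 mg change (true d1.5) | 6 mg change (true 1) | 6 mg minus placebo (true 1) | 1.5 mg minus placebo (true d1.5) |
|---|---|---|---|---|---|
| 0 | -0.33 | -0.33 | 1.00 | 1.33 | 0.00 |
| 0.25 | -0.42 | -0.08 | 0.92 | 1.33 | 0.33 |
| 0.5 | -0.50 | 0.17 | 0.83 | 1.33 | 0.67 |
| 1 | -0.67 | 0.67 | 0.67 | 1.33 | 1.33 |

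For effects in the same direction, the 1.5 mg change takes the wrong sign only when d1.5 < d6/3. With an off-treatment baseline in every period, the expected changes are 0, d1.5 and d6.

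**The case against.** The strongest reply is that the biased output may never be produced, for three reasons.

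- SAP 6.18 defines the safety baseline as pre-dose on each treatment day, which conflicts with SAP 6.2.
- SAP 6.2 also says that when a patient's baseline for a parameter is missing within a treatment period, nothing is derived for that period. Together these could mean that no laboratory change is calculated at all.
- SAP 6.18.2 and 6.18.5 name no change or shift, whereas the vital-sign, ECG and physical-examination sections do. The output shells, which might settle the matter, are in a separate document (SAP 1).

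This stands as far as certainty goes: a reader might infer that the bias is settled in the plan, and the documents do not support that. It does not dispose of the point. Protocol 10.4.7 names laboratory and Holter data in the paragraph that requires change and shift. SAP 6.4 speaks of post-baseline laboratory values, and SAP 6.19 does not list dropping the change outputs among its departures from the protocol. A pre-dose treatment-day laboratory value is not scheduled, and the Day 2 pre-dose Holter start follows Day 1 dosing. The rule that does yield a number yields the contaminated one.

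The reply is also right about importance. A reader might infer that the heart-rate findings or the formal safety tests are compromised. They are not touched by this gap: SAP 6.18.7 tests pulse rate and heart rate, which come from vital signs and ECG, and palpitations are recorded as adverse events. Laboratory and Holter data are descriptive. Unscheduled tests, allowed by protocol 7.4.2, could also give some patients a clean laboratory baseline.

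**Conclusion.** The gap in the schedule is a fact, and SAP 6.2 and 6.18 do not agree on how to fill it. If SAP 6.2 is programmed as written, the baseline is contaminated by the previous treatment in two of three periods for each completer. Placebo then shows an expected change of -(d6 + d1.5)/3, and both differences from placebo are one third too large. This rests on balanced completers, no period drift and full recovery in washout. It is a likely rather than certain result, because the SAP also supports deriving nothing.

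Two further readings go too far. A reader might call this drug carry-over, but the washout arithmetic shows that the drug is gone; the fault lies in which recorded value is used. The Day 4 laboratory sample is early post-treatment, while the Holter is recorded on treatment. A reader might also conclude that the low dose will show a reversed effect. That needs d1.5 < d6/3, and the documents give no size for either effect.

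Observed values by treatment remain interpretable. The SAP should be corrected, but the safety assessment does not depend on these outputs alone.

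**What to change.** Reconcile SAP 6.2 and 6.18 with a statement such as: for haematology, biochemistry and Holter parameters, a value recorded during or at the end of an earlier treatment period (Day 2-3 Holter, Day 4 laboratory sample) is never used as baseline. Then choose one of two options:

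- **Screening baseline.** Use the screening value for all three periods in the change and shift outputs.
- **Observed values only.** State that only observed values by treatment are reported and that no change or shift is derived. Record this in SAP 6.19 as a departure from protocol 10.4.7.

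The cost is a short SAP edit and some programming, with no new samples. The screening option has two drawbacks. By Day 1 of Period 3 the value is between 7 + 2 × (2 + 7) = 25 and 21 + 2 × (2 + 21) = 67 days old, before any rescheduling. It may also follow the salbutamol reversibility test, since protocol 6.1 lists that test ahead of Holter placement and blood sampling without saying that the list is a fixed order. Both could shift the mean change on every treatment. As one value common to all of a patient's periods, however, screening cancels in within-patient treatment contrasts. The end-of-study laboratory sample is also drug-free, but it follows all treatment and cannot serve as a baseline.

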6.18.3 Vital Signs

The AUC parameters will be calculated using the linear trapezoidal rule. The peak pulse rate will be computed as the maximum value in the 4 hours after dosing minus the pre-dose Day 1 baseline value.

Peak (measured in first 4 hours after dosing) and AUC_{0-4h} pulse rate will be derived.

Vital sign observed values and change from baseline by parameter (unit) will be summarised over time.

In addition, 'substantial' changes from baseline will be categorised as follows: change from baseline in systolic/diastolic blood pressure (BP) (systolic BP [>±40 mmHg], diastolic BP [>±20 mmHg]) and pulse rate [>±30 bpm]). The number

and percentage of patients with changes from baseline as categorised above will be summarised separately for positive and negative changes over time and at any postbaseline time point.

All vital sign data will be listed including change from baseline and flags for substantial changes from baseline.,

A listing of clinically significant vital signs recorded throughout the study will be provided.

Mean (±SEM) figures will be presented for changes from baseline blood pressure and pulse rate data for each treatment day. The three study treatments will be represented by different colours on the figures at each postdose timepoint.

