6.18.4 Electrocardiography

The AUC parameters will be calculated using the linear trapezoidal rule. The peak heart rate will be computed as the maximum value in the 4 hours after dosing.

Peak (measured in first 4 hours after dosing) and AUC_{0-4h} heart rate will be derived.

ECG data including QTcF and heart rate data will be summarised and listed.

Shift table in relation to the normal range from baseline over time for the absolute values will be presented for ECG data. Number and percentage of subjects will be presented for the change from baseline values. The absolute values will be categorised as: \leq 450 msec, >450 msec, >480 msec and >500 msec. The change from baseline values will be categorised as: increase >30 msec and increase >60 msec.

Mean (±SEM) figures will be presented for changes from baseline QTcF and heart rate data for Day 1 and Day 3 separately. The three study treatments will be represented by different colours on the figures at each postdose timepoint.

All ECG overall interpretation data will be listed. Abnormal ECG data will be listed separately.

6.18.5 24-Hour Holter Monitoring

All 24-hour Holter monitoring and parameter data will be listed. Data for time in AFIB percentage, supraventricular runs, total QRS complexes, ventricular runs, ventricular singles and RR > 2 seconds will be summarised.

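### SAP 6.2 takes ECG and vital-sign baselines from time-matched Day 1 readings, but Day 1 is a dosing day, so the planned change outputs lose their untreated reference

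*SAP*

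**What the plan says.** SAP 6.2 opens with a general rule. Baseline is the "last non-missing value (including scheduled and unscheduled assessments) prior to the patient receiving study treatment for each of the respective study treatments". It then makes a separate provision: "For ECG and vital signs, time-matched baselines from Day 1 of each Treatment Period will be used for the analysis of data".

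Other sections also speak to the baseline for safety data:

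- SAP 6.18, on continuous safety variables: "the change from baseline (pre-dose at each treatment day) to each post-dose time point will also be calculated and summarised". Protocol 10.4.7 has the same provision, but refers to the treatment visit rather than the treatment day.
- SAP 6.18.3 has peak pulse rate "computed as the maximum value in the 4 hours after dosing minus the pre-dose Day 1 baseline value".
- SAP 6.18.7 sets the covariate for the pulse and heart-rate ANCOVA as the value before the first dose of the period.

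Several planned outputs use a change from baseline without naming the baseline:

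- SAP 6.18.3: "figures will be presented for changes from baseline blood pressure and pulse rate data for each treatment day". The same section says that substantial "changes from baseline will be categorised as follows", with limits of 40 mmHg systolic, 20 mmHg diastolic and 30 bpm.
- SAP 6.18.4: figures of "changes from baseline QTcF and heart rate data for Day 1 and Day 3 separately", and "The change from baseline values will be categorised as: increase >30 msec and increase >60 msec".

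SAP 6.19, which lists departures from the protocol analysis, does not mention a time-matched baseline.

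**The concern.** Time-matching removes diurnal variation when there is an untreated day with readings at the same clock times. This trial has no such day. Tiotropium and the nebulised treatment are both given on the morning of Day 1 of each period (protocol Synopsis, 5.4.2 and 6.2.2), so every Day 1 reading after the pre-dose set is an on-treatment reading. Using those readings as the baseline subtracts the early treatment response from the later one, and on Day 1 it subtracts the response from itself.

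ECG and vital signs are named secondary endpoints (protocol 10.3.2). Protocol 1.2 mentions a non-clinical potential for hypotension and tachycardia, and small heart-rate increases at 12 to 24 mg. The change tables, change figures and threshold counts are where a reader would look for such effects.

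**Working it through.** The plan gives no figure of its own on this point, so the check is a count from the visit schedule.

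**Inputs.** Post-dose times in hours after the morning dose, per treatment period:

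| | Day 1 | Day 2 | Day 3 | Total |
|---|---|---|---|---|
| Vital signs (protocol 7.4.3) | 0.5, 1, 2, 4, 6, 8, 12 (7) | 0.5, 1, 2, 3, 4, 12 (6) | 0.5, 1, 2, 4, 6, 8, 24 (7) | 20 |
| ECG (protocol 7.4.5) | 2, 4 (2) | 2 (1) | 2, 4, 24 (3) | 6 |

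Protocol 3.1 describes Day 1 vital signs as running to 4 hours. I use 7.4.3, which agrees with the Synopsis, 6.2.3 and Table 4.

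**Formula.** Let X(d, t) be the reading on Day d at t hours, and X(1, 0) the Day 1 pre-dose reading. The rule as written gives X(d, t) − X(1, t). A pre-first-dose baseline gives X(d, t) − X(1, 0). On Day 1 the first expression is X(1, t) − X(1, t) = 0 for every patient in every arm.

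**Count under the rule as written.**

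| Result | Vital signs | ECG | Total |
|---|---|---|---|
| Day 1: reading minus itself | 7 | 2 | 9 |
| Days 2 and 3: on-treatment minus on-treatment | 5 + 6 = 11 | 1 + 2 = 3 | 14 |
| No Day 1 counterpart (Day 2, 3 h) | 1 | 0 | 1 |
| Match to Day 1 pre-dose by clock time only (Day 3, 24 h) | 1 | 1 | 2 |
| Total | 20 | 6 | 26 |

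So 9 + 14 + 1 = 24 of 26 post-dose times have no untreated time-matched value. If matching is strictly by hours since dosing, the two 24-hour readings have no match either, and the figure is 26 of 26.

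**Effect on a threshold count (arithmetic illustration, not a predicted effect).** Suppose QTcF at 2 h is 35 msec above the pre-first-dose value on both Day 1 and Day 3.

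- Rule as written: Day 1 change 35 − 35 = 0; Day 3 change 35 − 35 = 0. Neither is counted.
- Pre-first-dose baseline: 35 − 0 = 35 on both days. Both fall in the category above 30 msec.

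The same cancellation applies to the blood-pressure and pulse limits in 6.18.3.

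**Outputs not exposed.** Peak pulse and the pulse and heart-rate ANCOVA state their own pre-dose baseline. Peak heart rate in 6.18.4 is a maximum with nothing subtracted. Observed values, the absolute QTcF categories at each time, Holter data and adverse events involve no such change. The efficacy analyses define their own baseline in 6.11.

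**The case against.** The best defence is that time-matched was meant as period-matched: the Day 1 pre-dose value of the same period, rather than screening or Period 1. That reading agrees with the general rule in 6.2 and with the peak-pulse definition. It would explain why 6.19 lists no change. A reading that sets every planned Day 1 change to zero is also unlikely to be what the authors wanted. All this is fair as evidence of intent. It does not rescue the text, because it gives the word time-matched no role. The sentence follows the general rule as a specific provision for ECG and vital signs, so a programmer would normally let it override that rule.

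A reader might also infer that SAP 6.18 sets a further, competing baseline, each day's own pre-dose value, and that the SAP therefore leaves the baseline undetermined. On that reading the 6.18 baseline would differ from the pre-first-dose value at all 17 post-dose times on Days 2 and 3 (6 + 7 vital-sign, 1 + 3 ECG). The documents do not support this. SAP 6.12.1, 6.13.1 and 6.18.7 each explain the baseline of the treatment day as the value before the first dose of the period. Protocol 10.4.5 explains the baseline of the visit in the same way, and protocol 6.2 describes the visit as lasting about 72 hours. Elsewhere, for example in 6.10, the SAP uses treatment day for a calendar day. The wording of 6.18 is therefore loose, but it is not clearly a different baseline.

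The table and figure shells are a separate document and may show which baseline is programmed. That would limit the practical risk but would not correct the SAP text.

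**Conclusion.** The sentence in SAP 6.2 is wrong as written for this design. It conflicts with the general rule beside it, and with protocol 10.4.7 and SAP 6.18 once those are read through the documents' own explanations. It removes all content from the Day 1 change figures, and it can hide a sustained change in the QTcF counts above 30 and 60 msec and in the substantial blood-pressure and pulse counts.

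The reach is limited to descriptive change tables, figures and threshold counts for ECG and vital signs. It would be too strong to say that the safety inference or the efficacy results are at risk. The schedule counts show how many time points are affected, not how large any distortion would be. The documents give no basis for an effect in msec, mmHg or bpm, and none is claimed. The counts assume that the sentence is applied literally and that the protocol 7.4.3 and 7.4.5 schedules hold. This should be fixed before the outputs are programmed or, if that has already been done, checked against the shells.

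**What to change.** 1. Delete the time-matched sentence in SAP 6.2.
2. State in 6.2, 6.18.3 and 6.18.4 that the baseline for all ECG and vital-sign changes is the pre-first-dose Day 1 value of each treatment period, as 6.18.7 already has for the ANCOVA.
3. Add to 6.18 the explanation already used in 6.12.1, 6.13.1 and 6.18.7, so that treatment day there clearly means the value before the first dose of the period.

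The cost is wording in four sections and one derivation. No new data are needed, and no efficacy or inferential safety analysis changes.

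The downside is that changes are no longer matched for time of day. For means, the by-treatment summaries already planned in 6.4, which include the placebo period, let readers judge diurnal variation. They do not correct an individual patient's threshold count for it.
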